## 8.2 Withdrawal from Trial

Trial Participants have the option to completely withdraw from the trial at any time without giving a reason. Total withdrawal would occur in the circumstance that the participant decides to completely withdraw from all treatment aspects of the trial and does not agree to any further scheduled follow up assessments. The participants' total withdrawal must be documented in the medical records and transcribed onto the relevant CRF. No further information will be collected from this participant for the purpose of this trial.

## 9 STATISTICAL CONSIDERATIONS

### 9.1 Statistical Analysis

Treatment effect on wound size will be tested between treatment and placebo groups and across wound types by ANOVA.

Estimated number of 28 patients in 2 equal groups gives an 85% power at a significance level of 0.05 to detect an improvement of 40% in wound healing rates at 12 weeks (20% standard deviation). Based on preclinical studies, a 50% improvement is expected.

### 9.2 Analysis of the Objective

Primary objective

- To compare the proportion of patients achieving a 40% reduction in wound size at week 12 between Ixekizumab and placebo groups.

Secondary Objective

- To compare the average wound size reduction in treated versus placebo group.
- To compare the number and proportion of patients achieving wound closure.
- To compare in an actuarial survival analysis the time to closure between placebo and treatment group.
- To compare average pain score and reduction in pain score at 12 weeks (Pain score 0-10) between placebo and treatment group.
- To compare average Quality of life (QOL) (measured by DLQI) and improvement in QOL at 12 weeks between placebo and treatment group.
- Compliance with compression will be compared as a patient reported outcome.

\*these biological endpoints will depend on availability of funding

### 9.3 Analysis of Exploratory Endpoints

Comparisons between wound healing in the treatment ulcers vs participants receiving placebo. Differences in the ulcer size will be compared by ANOVA

- We will compare IL17 levels in wound fluid and biopsies between placebo and treatment group.
- We will compare Neutrophil infiltrating and wound macrophage phenotype change from M1 to M2 on immunostaining.

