#### **4.3.1 Inclusion Criteria**

1. Aged 18 years or older.
2. Patients who are willing to read or comprehend and signed a voluntary consent for research.
3. Patients with at least one venous leg ulcer defined as any break in the skin that had either been present for longer than 6 weeks or occurred in a person with a history of venous leg ulceration. Ulcers are judged purely venous if no other cause is suspected. The ulcer is required to be venous in appearance (moist, shallow, and of an irregular shape) and to lie wholly or partly within the gaiter region of the leg where varicosities or purpuric and pigmented skin can be identified.
4. Patients with Chronic Venous Ulcers that have failed to respond (<20% closure) to Standard Therapy including Compression 4 weeks

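### Ulcer size is to be tested by ANOVA with neither baseline ulcer area nor the ulcer-duration stratum in the model, and section 9.3 names ulcers in one arm and participants in the other

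*Protocol*

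**What the plan says.** - **Method for size.** Section 9.1 tests the treatment effect on wound size by ANOVA, between the groups and across wound types. Section 9.3 repeats the method: "Comparisons between wound healing in the treatment ulcers vs participants receiving placebo. Differences in the ulcer size will be compared by ANOVA". No covariate is named in either place. The wound types in 9.1 are not defined, and the trial enrols venous ulcers only, so that phrase does not identify the duration stratum.
- **Use of baseline.** The primary endpoint and the size secondary endpoint (sections 2.3.1 and 2.3.2) are reductions relative to initial size. Section 9.2 adds "To compare the average wound size reduction in treated versus placebo group".
- **Stratification.** Section 6 randomises in blocks of 4 within two strata, ulcer duration up to 6 months or longer, and justifies this by the link between duration and healing.
- **Data available.** Section 7.1 schedules an ulcer assessment at pre-screening and at each injection visit from the loading dose on. Section 7.2 has DLQI at baseline and at 12 weeks. Pain appears in neither section.
- **Unit.** Section 4.3.1 admits "Patients with at least one venous leg ulcer". No index ulcer is defined. Section 6 randomises patients, section 9.1 sizes the trial in patients, and section 9.2 counts patients for the responder and closure comparisons.

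**The concern.** Sections 4.3.1 and 4.3.2 set no limit on ulcer size, so starting areas may differ widely. With 14 patients per arm, chance imbalance in starting area is likely to be noticeable, and an ANOVA without that term leaves its effect in the comparison. It also leaves in the error term any variation that baseline area and ulcer duration could explain. The protocol itself treats duration as prognostic when it randomises, then names no term for it when it analyses. In a trial of 28 patients that precision is worth having.

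The wording of 9.3 raises a second point. If a patient with two ulcers contributed two observations treated as independent, the standard error would be too small.

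**Working it through.** **Inputs.** From the protocol: 28 patients, 14 per arm, significance level 0.05 (sidedness not stated; two-sided assumed). Not in the protocol, so assumed with a range: correlation r between baseline and week-12 values, 0.3 to 0.7; ulcers per patient m, 2 to 3; within-patient correlation (ICC), 0.3 to 0.8.

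**1. The plan's own figure.** Section 9.1 states "85% power at a significance level of 0.05" for 28 patients, "to detect an improvement of 40% in wound healing rates at 12 weeks (20% standard deviation". Read as a difference of 40 points with SD 20, the standardised difference is 2 and the noncentrality is 2 × √(14/2) = 5.29. Power is Φ(5.29 − 1.96) = 99.96% (99.9% by the t distribution), not 85%. That mismatch is a separate matter. It means only that the gain below has to be shown from a test that truly has 85% power at 14 per arm, which needs a standardised difference of 1.18 (two-sided t).

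**2. Variance factors** for a continuous outcome with equal variances at both times: week-12 value alone 1; change 2(1 − r); ANCOVA 1 − r². Change minus ANCOVA is 2(1 − r) − (1 − r²) = (1 − r)², which is never negative.

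| r | Week-12 only | Change | ANCOVA | ANCOVA cut vs week-12 only | ANCOVA cut vs change |
|---|---|---|---|---|---|
| 0.3 | 1 | 1.40 | 0.91 | 9% | 35% |
| 0.5 | 1 | 1.00 | 0.75 | 25% | 25% |
| 0.7 | 1 | 0.60 | 0.51 | 49% | 15% |

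The last column is 1 − (1 − r²)/[2(1 − r)] = 1 − (1 + r)/2.

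**3. In power and patients.** With baseline as the one covariate (25 df):
- Starting from a week-12-only test with 85% power, ANCOVA has 88.0%, 93.2% and 98.7% at r = 0.3, 0.5 and 0.7. The precision of 28 patients is reached with 28 × (1 − r²) = 25.5, 21.0 and 14.3.
- Starting from a change-score test with 85% power, ANCOVA has 96.0%, 93.2% and 90.1%.
- At r = 0 nothing is gained, and the lost degree of freedom takes 85.0% to 84.9%. A second uninformative term takes it to 84.8%.

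**4. Chance imbalance.** The SD of the difference in baseline means is √(2/14) = 0.378 SD. With probability 20% (two-sided) the arms differ by at least 1.28 × 0.378 = 0.48 SD. At r = 0.5 that moves an unadjusted week-12 comparison by 0.5 × 0.48 = 0.24 SD.

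**5. Percentage reduction.** If its correlation with log baseline area is q, the variance cut is q². The protocol gives no basis for q, and it may be small, so the table does not carry over to this endpoint. The stratum term may still help.

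**6. Unit of analysis, if ulcers were pooled as independent.** The design effect is 1 + (m − 1) × ICC. For m = 2 and ICC 0.5 it is 1.5, and the true two-sided error is 2[1 − Φ(1.96/√1.5)] = 11%. Over the assumed range it is 8.6% (m = 2, ICC 0.3) to 22% (m = 3, ICC 0.8).

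Pooling in the treated arm only, as 9.3 literally reads, with m = 2 and ICC 0.5: true variance 1.5/28 + 1/14 = 0.125 against an assumed 1/28 + 1/14 = 0.107. The ratio is 1.17 and the error 7%. The range is about 6% to 10%.

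**The case against.** Four arguments can be made against the point.

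*Baseline is already used.* This is largely right. A reader might infer from the bare ANOVA that baseline is ignored, but the primary and secondary size endpoints are relative to initial size, and the ulcer-size differences in 9.3 can be read as changes. No section says that raw week-12 area will be compared. What remains is that forming a reduction is not adjusting for baseline, and that no covariate is named.

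*An analysis plan that is not shown may settle the model.* This holds for pain and DLQI. A reader might infer that both are to be compared unadjusted, yet section 9.2 lists what is compared, for example "To compare average pain score and reduction in pain score at 12 weeks (Pain score 0-10) between placebo and treatment group", and names no test. For pain no baseline score is scheduled, so adjustment cannot be asked for as the schedule stands. The argument does not hold for ulcer size, where the protocol names the method twice.

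*The ulcers in 9.3 are loose wording.* Probably so. A reader might infer that several ulcers per person will enter as independent observations, but patients are the unit of randomisation, of the sample size and of the responder and closure counts. The error rates in step 6 show what the literal wording would permit, not what is planned.

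*The gain is assumed and leaves the primary endpoint alone.* The correlation is indeed assumed, and with a weak one there is little to gain. A reader might also infer that the power of the primary comparison suffers. That comparison is of responder proportions, so these figures do not apply to it directly.

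**Conclusion.** The point holds for ulcer size. Sections 9.1 and 9.3 fix an ANOVA that leaves out baseline area and the randomisation stratum, although both are collected and the protocol regards duration as prognostic. On an assumed r of 0.3 to 0.7, ANCOVA lowers the variance by 9% to 49% against the week-12 value alone and by 35% to 15% against the change. For percentage reduction the size of the gain cannot be fixed from the protocol and may be smaller. The cost is about two degrees of freedom.

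The ulcers-against-participants sentence in 9.3 is a wording error to correct. It matters because more than one ulcer is allowed and no index ulcer is named, but it does not prove a faulty analysis. Adjustment for baseline is advisable for DLQI, where no test is fixed and so nothing is wrong as written. This is a recommendation on efficiency and clarity for the continuous size outcome. It does not show that the primary analysis is invalid.

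**What to change.** 1. In sections 9.1 to 9.3, replace ANOVA of ulcer size with ANCOVA on one value per participant (percentage reduction or week-12 area), with treatment, ulcer-duration stratum and log week-0 area as terms. Delete or define the wound types in 9.1.
2. Reword 9.3 to compare participants on ixekizumab with participants on placebo.
3. Define one index ulcer per participant, selected by a written rule before randomisation and recorded on the case report form, and use it wherever ulcer size is analysed.
4. Where the DLQI model is specified, analyse the week-12 score with the baseline score as covariate.

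Cost: items 1, 2 and 4 change analysis wording only and use data already scheduled; the model in item 1 spends about two degrees of freedom out of 26. Item 3 needs a selection rule and one extra entry at baseline, so it has to be in place before patients are randomised.

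### The named ANOVA on ulcer size ignores the randomisation stratum and could lose power if some ulcers enlarge; a stratified rank test on percentage reduction is a cheap safeguard for this non-primary comparison

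*Protocol*

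**What the plan says.** - **Method, Protocol 9.1:** "Treatment effect on wound size will be tested between treatment and placebo groups and across wound types by ANOVA".
- **Method, Protocol 9.3 (exploratory endpoints):** "Differences in the ulcer size will be compared by ANOVA".
- **Secondary objective, Protocol 9.2:** "To compare the average wound size reduction in treated versus placebo group", with no test named on that line. Section 2.3.2 lists the matching endpoint as percentage reduction at week 12.
- **Primary objective, Protocol 9.2:** "To compare the proportion of patients achieving a 40% reduction in wound size at week 12 between Ixekizumab and placebo groups". This is a responder proportion and not the ANOVA outcome.
- **Power, Protocol 9.1:** "Estimated number of 28 patients in 2 equal groups gives an 85% power at a significance level of 0.05". The assumed effect is a 40% gain in healing, and the assumed SD is 20%.
- **Eligibility, Protocol 4.3.1:** "Patients with at least one venous leg ulcer", with no minimum or maximum area. Patients must show under 20% closure in the run-in. That rule has no lower bound, so an ulcer that is already growing qualifies.
- **Randomisation, Protocol section 6:** stratified by ulcer duration (up to 6 months or longer), in blocks of 4, because duration predicts healing.

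No transformation, baseline adjustment, rank method or duration term is named for the size comparison.

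**The concern.** Three features of the named analysis do not fit the data this design can produce.

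1. **Asymmetric outcome.** A healed ulcer scores 100% and cannot score more. An ulcer that triples scores -200%. With 14 patients per arm, one such value can shift an arm mean and inflate the residual variance.
2. **Wrong second factor.** Only venous ulcers are enrolled, so wound type has no evident levels. Ulcer duration, which the protocol itself calls prognostic and uses to stratify, is left out.
3. **Open scale.** Sections 9.1 and 9.3 speak of size, 9.2 of average reduction and 2.3.2 of percentage reduction. If the ANOVA were run on absolute week-12 area, variation in starting size would swamp the treatment effect.

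In a 28-patient trial the continuous size measure carries much of the efficacy information. At stake are the power of that comparison and whether the mean difference reflects more than one or two patients.

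**Working it through.** All tests are two-sided at 0.05 (the protocol does not state sidedness). The 40% and the 20% SD are read as percentage points of area reduction, since the protocol does not define their scale. Simulations used 5,000 trials per scenario (10,000 in the first two rows of step 4), so Monte Carlo error is at most √(0.25/5000) = 0.7 points per figure.

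**1. The plan's own power figure.** With 14 per arm, the standard error is 20 × √(2/14) = 7.56. The noncentrality is 40/7.56 = 5.29, and the t-test power on 26 df is 99.9%, not 85%. A true 85% corresponds to a difference of about 23.5 points (23.5/7.56 = 3.11). That mismatch is a separate matter. Here the two differences serve only as benchmarks.

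**2. Normal data, no outliers** (strata of 8 and 20 patients assumed):

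| Difference / SD | ANOVA | van Elteren |
|---|---|---|
| 40 / 20 | 99.9% | 99.7% |
| 23.5 / 20 | 85.5% | 81.8% |

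The rank test is equal in the first case and 85.5 - 81.8 = 3.7 points worse in the second.

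**3. A few enlarging ulcers.** By arithmetic, one ulcer at -200% instead of +40% moves its arm mean by 240/14 = 17.1 points, which is 17.1/40 = 43% of the planned effect. For power, assume a placebo mean reduction of 30 points, a treatment difference of 40, SD 20, values capped at 100, and k of the 28 ulcers, placed at random, enlarging by 50 to 150%:

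| k of 28 | ANOVA | van Elteren | Gap |
|---|---|---|---|
| 1 | 72.6% | 99.3% | 26.7 |
| 2 | 54.8% | 97.7% | 42.9 |
| 3 | 43.0% | 92.7% | 49.7 |

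With one ulcer enlarging by only 20 to 60%, the figures are 95.5% and 99.3%, a gap of 4 points.

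**4. Widely spread area ratios.** Assume the ratio of week-12 to baseline area is log-normal with log means -0.2 and -1.0 (median reductions 1 - e^-0.2 = 18% and 1 - e^-1 = 63%), and that a ratio below 0.05 counts as healed:

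| Log-SD | 0.5 | 0.6 | 0.8 | 1.0 |
|---|---|---|---|---|
| ANOVA | 96.3% | 87% | 59% | 35% |
| Unstratified rank test | 97.4% | 90% | 69% | 48% |
| Placebo ulcers that more than double | – | 7% | 13% | 19% |

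With van Elteren and strata of 12 and 16, the gap is nil at log-SD 0.3 to 0.5 and about 9 to 15 points at 0.8 to 1.0. At most about 2% of ulcers heal in this model, so the gap comes from the enlarging tail and not from a cluster of healed ulcers.

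These spreads are large. The placebo SD of percentage change is 100 × e^(-0.2+s²/2) × √(e^(s²) - 1). That is 65, 107 and 177 points for s = 0.6, 0.8 and 1.0, against the protocol's 20.

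**5. The duration stratum.** With a stratum effect of 0.6 on the log scale, unstratified ANOVA on percentage reduction rejects a true null in only 1 to 3% of trials, against about 5% for van Elteren. Without a stratum effect, van Elteren is 0 to 3 points below the unstratified rank test. With a 20-point stratum effect and 10% of ulcers enlarging, it is 2 points above (91.7% against 89.7%).

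**6. Absolute week-12 size.** Assume log-normal baseline area and a fractional reduction of mean 0.3 or 0.7 with SD 0.3:

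| Baseline log-SD | ANOVA | van Elteren |
|---|---|---|
| 0.5 | 66% | 72% |
| 1.0 | 28% | 49% |
| 1.3 | 16% | 39% |

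In the same model, percentage reduction gives 92% with ANOVA and 89% with van Elteren. On this point the scale matters more than the test.

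**The case against.** The strongest case against has four parts.

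- **No document shows that the data will be skewed.** The only spread given is an SD of 20, and under normal data with that SD ANOVA is as good or slightly better. The wide-spread scenarios imply SDs about three to nine times larger. This stands, and it makes the loss conditional.
- **ANOVA is valid here.** A reader might infer that outliers produce false positives. They do not: under the null in the wide-spread model it rejected in 3.5 to 4.7% of trials, and in about 3.6% with 10% of ulcers enlarging. The harm is lost power only.
- **The comparison is not primary.** A reader might infer that the trial's main conclusion is at risk, because 9.1 puts ANOVA beside the power statement. Section 9.2 makes the primary objective a responder proportion, in which one enlarging ulcer counts as one non-responder however much it grows.
- **Rank versus mean is partly a preference, and detail may sit in an unseen SAP.** This is fair for transformations and sensitivity analyses. It does not answer the protocol's own naming of wound type and omission of its stratification factor. Read with 2.3.2, the ANOVA may well be meant for percentage reduction, in which case step 6 does not apply; the wording in 9.1 and 9.3 leaves that open.

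It would also be wrong to credit stratification with the power gain. Ranking supplies nearly all of it when ulcers enlarge. Stratifying mainly respects the randomisation and restores the nominal error rate.

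**Conclusion.** The point holds as a minor, conditional improvement to a secondary and exploratory comparison. The mechanism follows from the protocol: no size limits, enlarging ulcers admitted, an outcome capped on one side only, and an analysis that omits the stratification factor. The size of the loss does not follow from the protocol, because it gives neither a size distribution nor an enlargement rate.

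- Normal data, SD 20: no loss from ANOVA, and the rank test costs up to about 4 points.
- Log-SD of the area ratio 0.8 to 1.0 (assumed): ANOVA loses about 9 to 15 points.
- 1 to 3 of 28 ulcers enlarging by 50 to 150% (assumed, with 40 points and SD 20): ANOVA loses about 27 to 50 points.
- Absolute week-12 size with widely varying baselines (assumed): ANOVA is much weaker still.

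The documents do not support saying that ANOVA will be driven by a few ulcers, only that it could be. The case for change is the imbalance: a small known cost against a possibly large loss, in patients selected for not responding to standard care.

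**What to change.** In sections 9.1 and 9.3:

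1. State week-12 percentage area reduction as the outcome, matching 2.3.2.
2. Analyse it with a van Elteren test stratified by ulcer duration (up to 6 months versus longer). Healed ulcers tie at the best rank, so zero area needs no special handling.
3. Report a Hodges-Lehmann difference with its confidence interval.
4. Remove wound type as a factor.
5. Keep a mean-based model with the duration term (ANOVA or ANCOVA) as a sensitivity analysis.

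Cost: wording only, with no change to data collection or sample size. The headline estimate becomes a location shift rather than a mean difference, and up to about 4 points of power are given up if the data prove normal.

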## **10 PATIENT REPORTED OUTCOMES AND HEALTH ECONOMICS**

### **10.1 Patient Reported Outcome Questionnaires**

The following Patient Reported Outcome (PRO) questionnaires will be used in this trial to assess Quality of Life (DLQI) outcomes in accordance with the time points as specified in Section 0:

#### **10.1.1 DLQI questionnaire**

The DLQI (see appendix Section 18.4) is a validated, copyrighted QOL assessment tool that is designed for use in adults and focuses on physical limitations rather than the psychological impact of the skin disease. It is self-explanatory and can be handed to the patient who is asked to fill it in without the need for detailed explanation. It may be used without seeking permission by clinicians for routine clinical purposes. The aim of the questionnaire is to measure how much the patients skin problem has affected their life over the last week. The DLQI is calculated by summing the score of each question resulting in a maximum of 30 and a minimum of zero. The higher the score the more quality of life is impaired.

#### **10.1.2 Pain Score questionnaire**

Pain score tool 1-10 will be used access participants level of pain during the trial.

## **11 TRIAL ADMINISTRATION AND QUALITY ASSURANCE**

### **11.1 Participating Centres**

Before activating the trial, participating sites are required to sign an agreement accepting responsibility for all trial activity which takes place within their site.

Sites may commence recruitment once the site agreement has been signed by all required signatories, the required trial documentation is in place, and a site initiation has taken place.

### **11.2 Data Acquisition**

Case Report Forms (CRF) will be used for the collection of trial data. The Trial Management Committee reserves the right to amend or add to the CRF template suite as appropriate. Such changes do not constitute a protocol amendment.

### **11.3 Data Management Plan**

A Data Management Plan (DMP) will be established in this study to outline the collection, use and plan for persevering and sharing data collected during this study. It will be recorded in the TMF.

### **11.4 Completion of the Study and Definition of Study End Date**

The study end date is deemed to be the date of last data capture.

### **11.5 Archiving**

Essential trial documents and source documentation (including medical histories, laboratory tests, treatment records and photographs) must be retained for 15 years after completion of the trial in accordance with ICH GCP Guidelines. Documents should be securely stored and access restricted to authorised personnel.

## **11.6 Study Monitoring**

The sponsor will be responsible for monitoring this study in accordance with ICH GCP guidelines and other appropriate regulatory guidelines. By signing this protocol, the investigator grants permission to the sponsor and appropriate regulatory authorities to conduct onsite and remote monitoring of all relevant study documentation essential documents and source data. To ensure accuracy of data captured on the case report forms, it is mandatory that the monitor have access to original source documents used in the completion of case report forms. During the review of these source documents, patient anonymity will be maintained with strict adherence to professional standards of confidentiality.

The sponsor will be responsible for monitoring relevant study documentation at regular intervals throughout the study, as defined by the pre-study risk-assessment and monitoring plan. The purpose of monitoring the study will be to verify adherence to the protocol, GCP and completeness and correctness of all case report form entries. The investigator agrees to cooperate with the sponsor to ensure that any items arising in the course of these monitoring visits are resolved.

